The second stage will only be conducted if enough external funds are ensured by using the results from the first stage as preliminary data. The second stage would consist of performing 16S rRNA on blood samples to analyze microbial composition in blood, and metabolomic analysis to evaluate the effect of the probiotic on gut-derived metabolites in blood and stools. The hypothesis of this second stage of the project is that the next generation symbiotic will change blood microbial composition as well as the presence and concentration of gut-derived metabolites in blood and stool samples. If relationships exists between changes in body composition, insulin sensitivity, depression, anxiety, or cravings (first stage variables) with blood microbial composition and derived-

metabolites (second stage variables), we could show not only a cause-effect relationship but also the mechanism of action through which the next generation symbiotic acts.

9) Background: Describe the theory or data supporting the objectives of the study and include a bibliography of key references as applicable.

Obesity is a strong risk factor for the development of the majority of the leading causes of death.¹ Recent research has pointed to the gut microbiota as a potential mechanism of action through which body weight can be regulated.² The gut microbiota of people with obesity has a lower alpha diversity³ and lower abundance of *Akkermansia muciniphila*.⁴⁻⁷

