60 participants ages 18-50 that have a BMI between 25.0-40.0 kg/m², who do not also have type 1 or type 2 diabetes mellitus (T1DM or T2DM) will be recruited. Exclusion criteria include: being vegetarian, vegan, carnivore, or keto; pregnancy or planning pregnancy during the study period; lactating women; having a history of inflammatory bowel disease, colon cancer; having been diagnosed with T1DM or T2DM; active cancer; currently participating in a weight loss intervention (dietetic or medication); use of antibiotics, antifungals, or antivirals in the last 3 months; currently taking metformin, GLP-1 agonists, insulin, or fiber supplement; having taken PPI, stimulant laxatives, probiotics, or immunosuppressants in the last month; history of recent (within 30 days) diarrhea illness (including bacterial or viral enteritis or enteric parasitic infection); having a known

hypersensitivity to any component of the study product; having an acute infection or inflammatory condition over the past 4 weeks; having >10% weight variation in the last 6 months; history of bariatric surgery in the past with exemption of laparoscopic band that has been removed.

12) Recruitment Procedure: Describe your recruitment strategies in great detail including how and where the potential participants will be approached and by whom. Will recruitment involve a point of contact on behalf of the study team? Who and how will recruitment material(s) be distributed? Describe precautions that will be taken to minimize the possibility of undue influence or coercion. Include copies of the recruitment emails, flyers, social media post, etc. in your submission as attachments or appendices following the recruitment guidelines.

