The triple blinding nature of this study means that participants, researchers (including the PI), and statisticians cannot be made aware of the randomization allocation. Therefore, debriefing to participants can only take part until after data has been analyzed. Once all participants have finalized their interventions and all data has been analyzed, researchers will contact back participants to verbally give them the debriefing statement and inform them which supplement/placebo they received.

14) Study Procedures: Provide a chronological description of the procedures, tests, and interventions that will be implemented during the course of the study. Indicate the number of visits, length of each visit, and the time it would take to undergo the various tests, procedures, and interventions. If blood or tissue is to be collected, indicate exactly how much in volume and all procedures that will be done with collected samples. Describe when, where and how collection will take place. Flow diagrams may be used to clarify complex projects. For Non-TCU study team members please explain their study team role in detail. If the study involved deception justify the use of deception and explain why deception is necessary to achieve the goals of the study. Explain if alternative methods not involving use of deception were considered and why these methods are not being used.

STAGE 1

For stage 1, participants will come to TCU on three days total:

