visit, depending on the order they enrolled, participants will receive the 3 bottles containing the assigned code. Participants will also be provided with two stool sample collection kits, a 3-day diet record form, a 3-day prescription of antibiotics (500 mg of generic Vancomycin every 8h), date for second appointment, and a start date for the antibiotic regimen. The 3-day antibiotic treatment provided prior to beginning the 12-week synbiotic intervention is given with the intention to increase the number of available bacterial niches (bacterial homes/space) and thus increase the engraftment of the newly ingested bacteria. Although participants will be asked to pay the cost of the generic antibiotic treatment initially (which should have an estimated cost of \$20-25), we will offset the cost of the antibiotic by providing the participants with a \$50 Amazon gift card in their second appointment, so they will not be responsible for any costs to participate in this study. This initial gift card is in addition to their \$100 Amazon gift card provided at the end of the study in appreciation for having taken part in this project. Their insurance will not be charged for any study-related testing; however, they are welcome to (but don't have to) use their insurance to buy the antibiotic. During this first visit, participants will have their 1) first 12h fasted blood collection and will be instructed to 2) fill out a 3 day food log before each stool sample collection, 3) collect a stool sample before the start of the antibiotic regimen, 4) collect a stool sample within 12-48 hours after the last dose of the antibiotic regimen, 5) bring both stool samples and diet records with them to the second appointment and, 6) fast 12 hours prior to the second appointment (refrain from the consumption of all food and liquids, except water). The first appointment is expected to take no greater than 45 minutes.

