For the second visit, participants will meet researchers at the Rickel building. This appointment is expected to take approximately 45 minutes and includes the completion of a DEXA scan, an air displacement plethysmography test (via BOD POD), body weight measurement, the Beck Anxiety and Depression Inventories, the RED-9 questionnaire, and a blood draw. Participants will turn in their first (before antibiotic prescription initiation) and second (after antibiotic prescription completion) stool samples and food logs to researchers. The blood draw will consist on 2 serum separation tubes (10 mL each), 1 EDTA tube (3 mL), and 1 Zymo tube (3 mL). The time to complete each test is approximately as follows: 10 minutes for the blood draw, 10 minutes for the anxiety and depression survey, 20 minutes for the DEXA scan, and 5 minutes for an air displacement plethysmography test. Air displacement plethysmography tests via the BOD POD will be used to measure body fat percentage. Participants will be asked to wear minimal clothes and no shoes for the air displacement plethysmography test. The DEXA scans will be used to measure fat mass, visceral fat, lean mass, and bone mineral density. The DEXA scan uses a two-sided low emission X-ray to quantify lean body mass, fat mass, and bone density. To conduct the test, participants will be asked to void their bladder, remove all metal objects (piercings, rings, etc.) and shoes, and will lay supine on a padded table for approximately 6 minutes while the scanner moves down the length of the participant's body. Measurements will be conducted by a General Electric Certified DEXA Operator ([name] or [name]). Blood samples will be collected using sterile techniques and only by qualified investigators ([name] or [name]). Blood samples will be used to measure fasting glucose, fasting insulin, and HbA1C. Blood will be sampled using venipuncture. The venipuncture samples will be collected using a traditional blood draw needle to extract blood from a vein in the antecubital region of the arm. Two 10 mL vials of blood will be collected, centrifuged to separate the serum. One of those tubes will be stored in a -80°C freezer in the Exercise Physiology Laboratory (Rickel 259) whereas the other will be transported to BioReference for fasting glucose and insulin analysis. The 3 mL for EDTA analysis will also be transported to BioReference for HbA1C analysis. The Zymo collection tube (3 mL) will be stored at the Rickel 259 building. All blood collection vials and plasma/serum containers will be

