
labeled using participant numbers (deidentified) for participant privacy. The leftover blood samples will be stored in the laboratory for 10 years from date of collection at which point they will be discarded as biohazard waste. Participants agree to allow their deidentified samples to be used for future research by signing the informed consent. These procedures have been approved by the TCU Institutional Biosafety Committee (IBC Protocol). At the end of the second appointment, participants will be provided with the 12 weeks of the probiotic+prebiotic supplement. Each person will receive 3 bottles (one per month) with the three of them having the same ID, this same ID will be used to identify all questionnaires and samples obtained from that person. This ID will also be different between each participant. Participants will also be instructed to 1) record everything they eat for 72 hours before stool sample collection, 2) collect a stool sample within 24 hours of finishing the last dose of the intervention, 3) bring the stool sample, diet record, and remnant of their supplement or placebo with them to the third appointment, and 4) fast 12 hours prior to the third appointment (refrain from the consumption of all food and liquids, except water).

The third and final appointment is expected to also take approximately 45 minutes and will include a replication of all tests conducted in the second appointment (completion of a DEXA scan, an air displacement plethysmography test [via BOD POD], body weight measurement, the Beck Anxiety and Depression Inventories, the RED-9 questionnaire, and a blood draw [consisting on 2 serum separation tubes of 10 mL each, 1 EDTA tube of 3.5 mL, and 1 Zymo tube of 3mL]). Participants will turn in their third and final stool sample, as well as the remnant of their supplements or placebo for analysis of adherence and compliance. Participants will receive a \$100 Amazon gift card at the end of the study in compensation for their time. After all stool samples have been collected, they will be sent in the same batch to the Alkek Center for Metagenomics and Microbiome Research (CMMR) at Baylor College of Medicine in Houston for posterior whole genome sequencing analysis.

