- 1) There are a total of 2 DEXA scans in this study. This will expose participants to low-dose radiation, the amount of radiation exposure is small and is about the same as one day of normal background radiation per scan. Exposure to ionizing radiation at low levels has the potential of causing cancer later in life. The risk of this occurring increases as the amount of exposure increases. The amount of radiation exposure in this study is very small and so the additional risk of causing radiation related effects does not change significantly by participating in this study. Prior to any body composition measurements, participants who are female and of childbearing age will be required to complete a pregnancy questionnaire. To minimize the radiation-related risks, females who become pregnant will be unenrolled from the study and will not undergo DEXA scanning. While radiation exposure is low, the consent form includes a statement that instructs participants to let the researchers know if they are in any other studies involving DXA scans in order to consider cumulative radiation exposure.
- 2) Although the antibiotic intervention is short (3 days) and might not be enough to cause gastrointestinal discomfort is possible that susceptible people may still experience gastrointestinal symptoms such as bloating and diarrhea. Secondary infections to antibiotic treatment, such as *Clostridioides difficile*, although unlikely are also possible. Short antibiotic interventions, however, cause minimal microbiota changes that are temporary and reversible (DOI: 10.1016/j.cell.2018.08.047). The antibiotic and dose chosen in this trial were the most highly used according to a systematic review our team published in 2022 in which we compared RCTs evaluating the effect of "antibiotic" versus "antibiotic + probiotics" (DOI: 10.1099/jmm.0.001625). Gastrointestinal discomfort at such short antibiotic interventions is unlikely, however, if present, symptoms tend to subside within a short period of time.
- 3) Likewise, supplementation with live bacteria strains (probiotics) and/or prebiotics may induce gastrointestinal discomfort secondary to microbiota composition changes.

- 4) Individual verbal treatment debriefing (placebo vs symbiotic) will take place after participant recruitment and data analysis have finalized as this is the time point in which we will reveal the randomization process.

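### Gastrointestinal symptoms are named as risks of both the antibiotic and the product, but the protocol text plans no systematic symptom or adverse-event collection and no comparison of symptoms between arms.

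*Combined protocol and SAP*

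**What the plan says.** **Risks (section 15).** Gastrointestinal discomfort from the antibiotic, the product or both is classed as a moderate risk. For the antibiotic, the text says it "is possible that susceptible people may still experience gastrointestinal symptoms such as bloating and diarrhea", and that secondary infections such as C. difficile "although unlikely are also possible". For the live bacteria and prebiotic it names gastrointestinal discomfort only. It describes these effects as unlikely or short-lived, and describes no monitoring, reporting route or follow-up for them.

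**Schedule (section 14).** "For stage 1, participants will come to TCU on three days total". The antibiotic comes first: "The 3-day antibiotic treatment provided prior to beginning the 12-week synbiotic intervention" is meant to help the ingested bacteria engraft, and no difference between arms is stated for it. The second visit follows the antibiotic and "includes the completion of a DEXA scan, an air displacement plethysmography test (via BOD POD), body weight measurement, the Beck Anxiety and Depression Inventories", then the RED-9, blood, and return of stool samples and food logs. The third visit "will include a replication of all tests conducted in the second appointment", with a stool sample and leftover product returned to assess adherence. The full supply is in participants' hands by the end of visit 2, so there is no resupply contact.

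**Analysis (section 19).** The comparisons within and between groups cover body composition, adherence, metabolic, dietary and psychological measures. No safety or tolerability variable is named.

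**The concern.** A trial that names a harm and has a placebo arm would be expected to ask about that harm in both arms. Here the risk section and the visit schedule do not meet. Three things are at stake.

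- **Tolerability.** The study is meant to supply preliminary data for further funding (section 16). On this text it could describe body composition, glucose measures and mood by arm, but would have no planned basis for saying how well the product was tolerated.
- **Attribution.** Symptoms before product start belong to the antibiotic period; symptoms afterwards could come from the product or linger from the antibiotic. Dated answers at visit 2 would separate the periods. Placebo would then show how much of the later burden goes with the product.
- **Interpretation of efficacy.** Section 11 excludes recent antibiotic use, diarrheal illness and acute infection at entry. The same events during the 12 weeks could affect microbiota and body composition results, and no visit is described as recording them.

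Unprompted reporting is a weak substitute. Section 17 withholds compensation from participants who withdraw or cannot finish, which may discourage some from raising problems.

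**Working it through.** The protocol gives no harm rate, power calculation or safety figure, so there is nothing to reproduce. The check is a count from the text, followed by an illustration of scale.

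**Step 1: count from sections 14, 15 and 19.**

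- Visits: 3.
- Symptom or adverse-event items listed at any visit: 0.
- Scheduled contacts between visits 2 and 3: 0, over 12 × 7 = 84 days of product.
- Safety variables in the analysis: 0.

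**Step 2: could something else in the plan fill the gap?** The returned product is used for adherence. The provision in section 17 for telling participants their results early concerns test and questionnaire results. Stool sequencing is batched after all samples are collected, so it cannot serve as clinical detection. The diarrhea item in section 11 is an entry criterion.

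**Step 3: what planned collection could show.** Section 11 gives 60 participants. The allocation ratio is not stated; 1:1, hence 30 per arm, is assumed from the aim of balanced groups in section 14. If everyone is asked and no event occurs, the one-sided 95% upper bound is 1 − 0.05^(1/n):

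- n = 30: 1 − 0.05^(1/30) = 0.095, or 9.5% per arm.
- n = 60: 1 − 0.05^(1/60) = 0.049, or 4.9% overall.
- n = 25 per arm (assumed dropout): 1 − 0.05^(1/25) = 0.113, or 11.3%.

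**Step 4: what a comparison between arms could show.** The symptom rates are assumptions, with 30 per arm and two-sided 0.05 (section 19 gives 0.05 without sidedness). Normal-approximation power is Φ[(|p1 − p2| − 1.96 × SE0)/SE1], where SE0 = √(2p̄(1 − p̄)/n), p̄ is the mean of p1 and p2, and SE1 = √([p1(1 − p1) + p2(1 − p2)]/n).

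For 10% vs 30%, SE0 = √(2 × 0.2 × 0.8/30) = 0.1033 and SE1 = √((0.09 + 0.21)/30) = 0.1000. Power is Φ[(0.2 − 0.2024)/0.1000] = 49%.

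| Assumed rates | Normal approximation | Fisher exact |
|---|---|---|
| 10% vs 20% | 19% | 10% |
| 10% vs 30% | 49% | 37% |
| 10% vs 40% | 78% | 71% |
| 20% vs 50% | 69% | 60% |

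**Step 5: unprompted reporting only.** If half of the true 10% vs 30% cases are reported in each arm, the observed rates are 5% vs 15% and power falls from 49% to 25%. If 30% are reported (3% vs 9%), it is 16%.

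So planned collection would support estimates with intervals, and only a large difference would be likely to reach significance. That makes estimation the right purpose for the form.

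**The case against.** The strongest reply is that the visit list is not exhaustive. Section 15 requires a pregnancy questionnaire before body composition measurements, and that form is absent from the visit descriptions in section 14. Section 14 cites a separate checklist, and section 20 refers to a consent document and data-collection forms submitted as separate files. A symptom item or reporting instruction could sit in any of these. This stands as a limit: the finding is that the protocol text describes no systematic collection. It does not answer the absence of any safety variable in section 19 or of any scheduled contact during the 12 weeks.

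A second reply is that 60 people cannot give a sensitive test of harms. Step 4 bears this out, but it argues for description with intervals, which still needs data.

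A reader might also infer more than the documents support:

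- **That C. difficile is named as a product risk.** Section 15 ties it to the antibiotic only.
- **That antibiotic harms could be compared between arms.** The antibiotic precedes the product with no stated arm distinction, so its symptoms are separated from later ones by date. Only visit 2 to visit 3 symptoms have a contrast by arm.
- **That sections 11 and 15 conflict**, because "history of recent (within 30 days) diarrhea illness (including bacterial or viral enteritis or enteric parasitic infection") excludes a person at entry while the antibiotic may cause diarrhea afterwards. Section 11 sets recruitment criteria. The same list excludes antibiotic use in the previous three months, which could not be re-applied after the protocol itself supplies an antibiotic. There is no contradiction to resolve.
- **That the stage 2 hypothesis that "the next generation symbiotic will change blood microbial composition" signals an infection risk.** It concerns sequencing of stored blood in a stage that depends on funding, and the documents draw no link to infection or fever.

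**Conclusion.** The concern holds in this form: gastrointestinal harms are named for the antibiotic and the product, and the protocol text plans no systematic way to record them and no comparison by arm. Its size is zero listed symptom items across three visits and zero scheduled contacts over 84 days of product, in 60 people. The plan therefore forgoes even simple bounds of about 9.5% per arm or 4.9% overall for zero events, which assume 30 per arm, full follow-up and everyone being asked.

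It would go too far to say that harms will go undetected or that the trial must end with no harms data. Unprompted reports are possible, and the unseen forms may contain relevant items. The symptom and reporting rates in the working are assumptions for scale. The change should be made: it is inexpensive, and the information cannot be recovered reliably afterwards.

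**What to change.** Add one short symptom and adverse-event form covering bloating, diarrhea with onset and duration, infection, non-study antibiotic use or medical care, and missed doses.

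- **When:** at visit 2 before product starts, and again at visit 3. Optionally send it once in between, using the email or phone number held from screening (section 13).
- **Reporting:** present visit 2 answers for all participants together, as antibiotic-period symptoms and as the baseline. Tabulate visit 2 to visit 3 symptoms by arm, with the difference and its confidence interval, and state that this is descriptive.
- **Text:** name the form in section 14 and the safety variables in section 19. If a submitted questionnaire or the consent form already covers part of this, cite it there.

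How individual symptoms are handled clinically is outside this point, and no rule is proposed. The cost is a few minutes at two visits planned at about 45 minutes each, form review by the existing team, one message per participant if the optional contact is used, and an IRB amendment.

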In the first visit, participants will come for 45 minutes to the Rickel Department where they will receive a complete explanation of the protocol and will process to sign the "Informed Consent to Participate in Research and Authorization to Collect, Use, and Share their Health Information" if agreeing to participate. Participants' height and weight will be measured to ensure they meet BMI inclusion criteria. Height will be measured using a standard stadiometer and weight will be measured using a standard calibrated digital scale. Their race will be asked to help in data interpretation. Height, weight, race and other information relevant to antibiotic prescription such as date of birth, allergies to medications, and preferred pharmacy will be collected at this time point using our document titled "checklist 2". All symbiotic and placebo bottles will be entirely similar with exemption of individual codes that will vary every 3 bottles. This is because each participant will be provided at the beginning of the study with 3 bottles (with similar code) to ensure enough supply for the 12-week supplement intervention. The company Pendulum will perform an *a priori* randomization of the entire study by using blocked randomization with randomly selected blocked sizes with the intention to reduce bias and ensure balance between groups. This randomization will be added into an Excel document in which they will specify the order of the participant in column 1 (example: Participant 001, Participant 002), the code of the bottles in column 2, and the interpretation of the code (placebo vs probiotic) in column 3. A researcher, independent from this study ([name]), will save in different protected locations (Box, secured laptop, protected USB) the randomization document. [name] will share with [name] an Excel document containing column 1 and column 2 of the provided document (the order of participant and the code of the bottles, without the interpretation of each code). [name] will use the supplement code as the participants' IDs and study data will be added to this Excel document. Both documents, from, [name] and from [name], will be merged at the end of the study, once data has been analyzed to figure out the intervention group to which each participant belonged. During the first

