If participants withdraw from their study the data collected up to that point will remain available for research purposes with the intention to use intent to treat analysis. Blood and stool samples will be stored in [name] lab located within the Rickel building room 259. For the first stage of the project, blood samples will be analyzed at [name] lab room 259. Once the Nutritional Sciences Department laboratory has been finalized, samples will be transferred to the Nutritional Sciences Department and further storage and analyses could take place here (BASS, room 1203). If enough funds become available to perform the second stage of the study, blood and stool samples (which will be identified by fabricated ID) will be sent to Baylor College of Medicine and to Metabolon for posterior 16S rRNA/WMS and mass spectrometry analyses, respectively. For statistical analysis of the first stage, two sample T-tests will be used to compare within (pre- versus post- values on each group) and between-group (placebo versus probiotic) differences in body composition, adherence, metabolic, dietary, and psychological variables. SPSS will be used for statistical analysis. A p value <0.05 will be considered as statistically significant. Dietetic variables collected via the NCI Automated Self-Administered 24-hour Dietary Assessment Tool including protein, carbohydrate, fat, and fiber will be controlled statistically in the case that significant intra-individual or between-group differences are observed.

20) Check List for the Items That Need to be Submitted: Please submit protocol and consent documents separately in MS word, supplemental documents (interview guides, surveys, recruitment materials etc. can be submitted as separate pdfs) before submitting the materials electronically to the IRB. To prevent any delay in the approval of your protocol, use the most recent template for the protocol, consent document, and HIPAA form by downloading them from <https://research.tcu.edu/research-compliance/irb/irb-forms-templates/> each time you prepare your materials.

a. Protocol	X
b. Consent document	X
c. Protecting Human Research Participants Training complete for each investigator	X
d. Recruitment flyers, letters, ads, etc.	X
e. Questionnaires or other documents utilized in screening and data collection	X

Principal Investigator Assurance

21) By signing below, I certify to the following:

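### Intention-to-treat is intended, but the between-group t-test has no baseline-outcome adjustment, does not say post value or change, and by default would use only participants with visit-3 data.

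*Combined protocol and SAP*

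**What the plan says.** Section 19 of the combined protocol and SAP keeps the data of participants who withdraw, which "will remain available for research purposes with the intention to use intent to treat analysis". It then names the method: "two sample T-tests will be used to compare within (pre- versus post- values on each group) and between-group (placebo versus probiotic) differences". This covers body composition, adherence, metabolic, dietary and psychological variables, in SPSS, at p below 0.05. The within-group part is described as pre against post. The between-group part is described only by the two arms. One adjustment is foreseen: protein, carbohydrate, fat and fibre intake "will be controlled statistically in the case that significant intra-individual or between-group differences are observed". No model is named for it.

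Section 14 (Study Procedures) sets the measurement times. The second visit, before product, "includes the completion of a DEXA scan, an air displacement plethysmography test", as well as weight, the Beck inventories, RED-9 and blood. The third visit, after 12 weeks, "will include a replication of all tests conducted in the second appointment". No outcome visit lies between them. Weight and a fasting blood sample are also taken at visit 1. A food log is requested before each stool sample, so two logs precede product. The allocation file and the study data "will be merged at the end of the study, once data has been analyzed".

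**The concern.** The stated principle and the named method do not meet. An intention-to-treat analysis has to say what happens to a randomised participant whose outcome is missing. The section does not say, and a t-test has no means of including that person.

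The between-group test could be run on post values or on changes. These differ in precision and in their response to selective loss, and neither is better at every pre-post correlation. The pre-product value is collected for most outcomes but is not used as a covariate. With the sample fixed at 60, the trial could give up precision that its own data would supply, and the choice of quantity could be made after the results are seen. The wish to control for diet already requires a linear model, because a t-test cannot hold a covariate.

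**Working it through.** **Inputs.** Total sample 60 (section 11). Significance level 0.05 (section 19). Assumed, because the documents do not state them: 1:1 allocation (section 14 says only that blocking should give balance), a two-sided test, 80% power, pre-post correlation r, and attrition. The plan gives no effect size, SD, power or dropout rate for the 60, so there is no figure of its own to reproduce. What follows is illustration.

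**Step 1: who enters the test.** A participant with visit 2 but not visit 3 has no post value and no change, so drops out of either t-test unless a value is imputed. The plan neither specifies nor forbids imputation.

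**Step 2: precision.** With equal variance before and after, set to 1, the residual variance is:
- post value: 1
- change: 2 − 2r
- ANCOVA: 1 − r²

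The detectable difference (noncentral t) is 0.736 SD at 30 per arm and 0.826 SD at 24 per arm (20% loss), each multiplied by the square root of the residual variance. For example, at r = 0.8 and 30 per arm, change gives 0.736 × √0.40 = 0.47 and ANCOVA 0.736 × √0.36 = 0.44.

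| r | 30 per arm: post / change / adjusted | 24 per arm: post / change / adjusted |
|---|---|---|
| 0.3 | 0.74 / 0.87 / 0.70 | 0.83 / 0.98 / 0.79 |
| 0.5 | 0.74 / 0.74 / 0.64 | 0.83 / 0.83 / 0.72 |
| 0.8 | 0.74 / 0.47 / 0.44 | 0.83 / 0.52 / 0.50 |
| 0.95 | 0.74 / 0.23 / 0.23 | 0.83 / 0.26 / 0.26 |

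The degree of freedom spent on the covariate does not change these at two decimals. As sample-size ratios at r = 0.8, post values need 1/0.36 = 2.8 times the participants of the adjusted analysis, and change scores need 0.40/0.36 = 1.1 times.

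**Step 3: bias from selective loss.** Simulation with no true effect and 2 million draws per arm: 20% loss in the active arm following a logistic curve (slope 1.0 per SD), and 20% random loss in the placebo arm. Bias in SD:

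| Loss depends on | r | Post | Change | Adjusted |
|---|---|---|---|---|
| Baseline | 0.5 | −0.086 | +0.086 | 0.000 |
| Baseline | 0.8 | −0.139 | +0.034 | 0.000 |
| Visit-3 value | 0.5 | −0.172 | −0.086 | −0.131 |
| Visit-3 value | 0.8 | −0.173 | −0.034 | −0.064 |

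At 24 per arm the standard error is √(2 × residual variance / 24). For the adjusted analysis at r = 0.8 this is √(0.72/24) = 0.173, and the bias is 0.064/0.173 = 0.37 standard errors. The type I error for visit-3-driven loss (normal approximation; post/change/adjusted) is then about 9.2%/5.4%/6.6% at r = 0.8 and 9.3%/6.1%/8.3% at r = 0.5. A steeper slope of 2 at r = 0.8 gives about 14.7%/5.9%/9.0%.

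**The case against.** Several points on the other side stand.

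- A reader might infer that the plan restricts the analysis to visit-3 attenders. It does not say so; this is only what a t-test does by default when nothing else is specified.
- A reader might call the analysis wholly unadjusted. That is too broad, because conditional control for diet is planned. What is missing is adjustment for the baseline outcome.
- A reader might take the 2.8-fold ratio as the expected gain. It arises only if post values are meant and the correlation is near 0.8. If changes are meant, which the wording allows, the gain is 1.1-fold at 0.8 and negligible at 0.95.
- ANCOVA is more biased than change scores in the simulations where loss depends on the visit-3 value.
- Evidence for differential loss is thin. Section 15 attributes gastrointestinal discomfort to the antibiotic, the synbiotic or both; all participants receive the antibiotic, and section 9 describes the product as tolerable in a pilot.
- Stage 1 is exploratory and meant as preliminary data, which tempers the consequence.

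None of this supplies the missing specification. Nor does it make a change-score t-test safe by default: at r = 0.3 it is less precise than post values, and at r = 0.5 it has no precision advantage and the same size of bias under baseline-driven loss.

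**Conclusion.** The point holds in this limited form: intention-to-treat is named without a way to handle missing visit-3 values, the between-group quantity is not chosen, and the available baseline is not used. Baseline adjustment is at least as precise as either t-test across the correlations examined, apart from the one degree of freedom. Its advantage over change scores shrinks from 0.70 against 0.87 SD at r = 0.3 to nothing visible at 0.95.

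Two stronger conclusions would not be justified. One is that change scores, or adjustment, make selective loss unimportant: at r = 0.5 with visit-3-driven loss, adjustment removes only about a quarter of the post-value bias (0.131 against 0.172 SD). The other is that the bias and type I figures are limits. They are scenarios, since the documents give no correlation or attrition.

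This is an improvement that should be made, not a flaw that invalidates the trial. Section 14 also describes the bottles as handed over at visit 1 and again at the end of visit 2. Those passages need reconciling, but that is a separate matter and this point does not rest on it.

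**What to change.** In section 19:

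1. For body composition, metabolic, psychological and dietary outcomes with a pre-product value, replace the between-group t-test with ANCOVA of the visit-3 value on the pre-product value, analysed as allocated. Keep the two-group comparison for adherence, which has no baseline.
2. Name visit 2 as the baseline where visit 1 also has a measurement (weight, fasting blood), and name which of the two pre-product food records is the dietary baseline.
3. State how missing visit-3 values are handled, and report two sensitivity analyses: change scores, and a shift of the missing values in one arm. A shift of 0.5 SD moves the estimate by 0.10 × 0.5 = 0.05 SD at 10% loss and 0.20 × 0.5 = 0.10 SD at 20%.
4. Fix the analysis set in writing before the codes are merged.

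The cost is a short rewording with IRB approval and one degree of freedom. SPSS runs ANCOVA, and the data are already planned. The limits should be stated with it. ANCOVA removes bias when loss depends on baseline but not when it depends on the visit-3 value, where change scores were less biased in the simulations; hence both are reported. It recovers no missing visit-3 information.
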